## **1 Study title, version number, version date**

### **1.1 Study title**

Influence of flat-knitted compression stockings class I/II on the morphology of venous malformations

- Is there a therapeutic effect?

### **1.2 Version number**

Version 1.0

### **1.3 Version date**

18.10.2017

## 2 Project summary

Diseases with vascular malformations are rare and often congenital, affecting patients of all ages. Depending on their extent and localization, they can cause discomfort and, especially if activity is restricted, lead to loss of or reduced quality of life.

The therapy is usually reserved for a few specialized centers and includes interventional sclerotherapy as well as conservative therapy by compression with appropriate compression stockings. However, there are currently no study-based recommendations for this approach.

The aim of this study is to prove a therapeutic effect of compression therapy using flat-knitted compression stockings on venous malformations of the extremities and to derive from this a therapy recommendation in connection with an improvement in the health status and quality of life.

For this purpose, patients with a confirmed venous malformation of the upper or lower extremity independent of previous therapy will be included. We will investigate patients with epi- and/or subfascial localization of the venous malformation independent of the local extent (cross-articular or not).

### 3.2 Sponsoring

Department of Vascular Surgery, University Hospital Erlangen.

The company *medi* from Bayreuth, Germany, finances the study, but does not function as a sponsor.

## 4 Scientific background

Vascular malformations are a rare disease with a prevalence of 1.5% in the whole population. 2/3 of peripheral vascular malformations are venous malformations, of which 40% are located at the extremities.

They develop congenitally and are characterized by growth proportional to body growth. Hormones (puberty, pregnancy), infections, operations, traumas stimulate growth. They do not show any regression tendencies.

Depending on their localization and extension, they can lead to considerable discomfort with limited physical activity and loss of quality of life.

In Germany, the therapy of venous malformations lies within the responsibility of a few specialized centers and depends on the physical impairment and subjective symptoms. In addition to interventional sclerotherapy, conservative therapy is performed in the form of compression therapy with appropriate compression stockings. To date, however, there are no study-based investigations and recommendations for this kind of therapy.

The study is intended to investigate the influence of flat-knitted compression stockings of different compression classes (class I and II) on the morphology (volume behavior) of venous malformations and to derive a therapeutic recommendation. The hypothesis is that a sufficient compression effect is already present in stockings of compression class I. We anticipate a relevant effect on the volume of the malformation under this kind of treatment. Furthermore, it is assumed that the effect of the compression therapy occurs immediately after the application of compression.

## 5 Study objectives

The aim of this study is to prove a therapeutic effect of compression therapy using flat-knitted compression stockings on venous malformations of the extremities and to derive from this a therapy recommendation in connection with an improvement in the health status and quality of life.

### 5.1 Primary/secondary objectives and hypotheses

#### *Primary hypothesis:*

The hypothesis is that a sufficient compression effect with volume relevance to the malformation is already present in compression class I.

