**Primary objective:**

- Determination of volume difference of the malformation by use of non-invasive measurements (Perometry, MRI)

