## 6 Target parameters

### 6.1 Primary target:

- Volume of affected extremity(ml)
  - *This target is measured non-invasively by perometry and MRI*

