## **11 Biometrics**

Continuous variables are given as means with standard deviation. Categorial variables are given as frequencies and percentage. Although making use of a crossover design, we do not expect any carryover or period effects due to the nature of the treatments. Therefore, differences between the treatments and baseline measurements are evaluated using Wilcoxon signed rank tests. Moreover, linear regression analysis is used to adjust for variations in

baseline measurements for the direct comparison of compression classes. A p-value below or equal to 0.05 is considered to indicate statistical significance.

All results will be calculated using R version 3.5.1 (R Foundation for Statistical Computing, Vienna, Austria).

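### The primary hypothesis is that class I is sufficient, but the planned tests can show only some effect or a class difference; no interval, relevance threshold or margin is planned

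*Combined protocol and SAP*

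**What the plan says.** Section 5.1 gives the primary hypothesis: "a sufficient compression effect with volume relevance to the malformation is already present in compression class I". Section 4 makes the same claim and adds: "We anticipate a relevant effect on the volume of the malformation under this kind of treatment". Sections 2, 4 and 5 all say that a therapy recommendation is to be derived from the results.

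No section turns *sufficient* or *relevant* into a quantity. The primary objective (section 5.1) asks only for a volume difference, and the primary target (section 6.1) is limb volume in ml. There is no minimum reduction, no share of the class II effect, no responder rule and no margin.

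Section 11 contains the whole analysis plan:

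- Descriptive reporting: "Continuous variables are given as means with standard deviation".
- Against baseline: "differences between the treatments and baseline measurements are evaluated using Wilcoxon signed rank tests".
- Between classes: linear regression, adjusting for variations in "baseline measurements for the direct comparison of compression classes".
- Criterion: "A p-value below or equal to 0.05 is considered to indicate statistical significance".

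It mentions no confidence interval and no equivalence or non-inferiority test. It does not say which analysis decides the primary hypothesis. Section 8.2 plans about 25 patients, with no derivation.

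**The concern.** The hypothesis makes two claims that need a reference value. An effect that is sufficient and relevant to volume must be at least some size. The word *already* suggests that little is lost by using the lower class instead of the higher one.

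Both planned analyses are tests of no difference. A significant result against baseline says that the shift is not zero; it does not say that the shift is large enough. A non-significant class comparison says that the data do not exclude equality; it does not say that they exclude a meaningful advantage of class II. A significant class II advantage would not settle the matter either, because without a threshold it does not show that class I falls short.

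At stake is the basis for the therapy recommendation. If p-values are the only planned output, whoever writes up the trial must decide after seeing the data what counts as sufficient.

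**Working it through.** **Is there a figure to reproduce?** No. The 25 patients in section 8.2 come without power, effect size, SD, margin or dropout. The calculations below are illustrations.

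**Inputs**
- n = 25 (section 8.2).
- Significance level 0.05 (section 11); two-sided is assumed, as sidedness is not stated.
- Paired data: on day 28 each patient is measured without a stocking and then with each class (section 9.2).
- Unit: the SD of the within-patient difference (assumed, because the documents give no SD). Differences are taken as normal.
- Paired tests stand in for the baseline-adjusted regression. Section 11 does not say whether that regression keeps the pairing.

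**Step 1. Precision.** The 95% CI half-width is t(0.975; 24)/√25 = 2.064/5 = 0.413 SD. An observed mean difference just above 0.413 SD is therefore significant by paired t, with a lower limit just above zero. That supports some effect but says little about relevance. Conversely, a non-significant class difference near zero has an interval of roughly −0.41 to +0.41 SD.

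**Step 2. How often a true class II advantage is missed.** For a true advantage d, the paired t statistic follows a noncentral t distribution with 24 degrees of freedom and noncentrality d√25 = 5d. The miss rate is the probability that its absolute value stays below 2.064. The Wilcoxon figures come from simulation with normal data.

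| True advantage d (SD) | Noncentrality 5d | p > 0.05, paired t | p > 0.05, Wilcoxon |
|---|---|---|---|
| 0.3 | 1.5 | 70% | 71% |
| 0.4 | 2.0 | 52% | 54% |
| 0.5 | 2.5 | 33% | 36% |

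**Step 3. What a sufficiency claim against class II would require.** Suppose class I is declared sufficient when the 95% CI for class II minus class I excludes a loss of m SD (one-sided level 0.025), and the classes are truly equal. Power at n = 25 is P(T > 2.064), with T noncentral t, 24 degrees of freedom and noncentrality 5m.

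| Margin m (SD) | Power at n = 25 | Patients for 80% power |
|---|---|---|
| 0.2 | 16% | 199 |
| 0.3 | 30% | 90 |
| 0.4 | 48% | 52 |
| 0.5 | 67% | 34 |
| 0.6 | 82% | 24 |

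So 25 patients give 80% power for such a claim only if the margin is about 0.6 SD or wider.

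**The case against.** The best defence is that the trial asks a simpler question. The title asks whether there is a therapeutic effect, section 5 aims to prove one, and the primary objective is to determine a volume difference. The within-patient test of class I against no stocking answers that. This stands: the planned tests are not useless, and the regression could also show a significant class difference. But the stated primary hypothesis goes further than any effect, and that further part is left untested.

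Three stronger readings are tempting, and the documents do not support them.

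- *A reader might infer that the plan will declare class I sufficient when it beats baseline and does not differ significantly from class II.* Section 11 contains no such rule. The fair criticism is that no rule links the tests to the hypothesis and nothing excludes that one.
- *A reader might infer that the trial will probably overlook a clearly better class II.* With no SD and no relevance threshold, an advantage of 0.3 to 0.5 SD cannot be called clear or trivial. At 0.5 SD the miss rate is about one in three. The miss rates also cover only the class comparison; a joint rule that additionally required significance against baseline could not be met more often.
- *A reader might infer that trivially small percentage reductions would be called significant.* That conversion needs a paired SD in percent, which the documents do not give. It would also depend on whether the volume is that of the limb or of the malformation, and the sections use both.

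It is also true that section 11 assigns the Wilcoxon test to comparisons with baseline and a regression to the class comparison. The miss rates in the working are therefore a proxy for the planned analysis.

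**Conclusion.** The point holds as a mismatch between hypothesis and analysis. Followed as written, section 11 can establish that class I has some effect on volume or that the classes differ. It cannot establish sufficiency, because there is no interval, relevance threshold or margin against which to judge it. This rests on the text alone and needs no assumption about variability.

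The size is illustrative. Under paired, normally distributed differences and 25 evaluable patients, a non-significant class comparison remains compatible with a class II advantage of about 0.4 SD, and a true advantage of that size is missed in roughly half of trials. What this means in ml cannot be stated from the documents. Because the gap concerns the primary hypothesis and the recommendation to be drawn from it, it should be closed before the data are analysed.

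**What to change.** In section 11:

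1. Make the primary result two within-patient volume differences from day 28: class I minus no stocking, and class II minus class I. Give each with a 95% CI, either Hodges-Lehmann or from a model that keeps the pairing.
2. State that a non-significant class difference will not be read as evidence that class I is sufficient.
3. Limit the conclusion to the estimates and their intervals, unless a relevant reduction and a margin against class II are fixed and justified before analysis. If they are, claim sufficiency only when the interval for class I excludes reductions smaller than the relevant one and the interval for class II minus class I excludes a loss larger than the margin.

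The threshold and margin are optional. The documents offer no basis for either, and reporting estimates with intervals is a sound result without them.

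The cost is a few sentences in section 11 and a few lines of R; the day 28 measurements are already planned. The downside is that a sufficiency claim becomes harder to make. If the classes are truly equal, 25 patients give about 16% to 48% power for margins of 0.2 to 0.4 SD, and about 82% at 0.6 SD.

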**Secondary hypotheses:**

Furthermore, it is assumed that the effect of the compression therapy occurs immediately after the application of compression and has an effect on the patient's quality of life.

**Primary objective:**

- Determination of volume difference of the malformation by use of non-invasive measurements (Perometry, MRI)

**Secondary objective:**

- Determination of volume difference of the malformation immediately after the application of compression by use of non-invasive measurements (Perometry, MRI)
- Determination of the quality of life by the questionnaire SF-12
- Determination of handling and wearing comfort of compression stockings in everyday life by the questionnaire "*Tragekomfortbogen*" (comfort of wearing questionnaire)

## 5.2 Study type

This is a prospective, monocentric, double-blinded, non-invasive, interventional single group study.

## 6 Target parameters

### 6.1 Primary target:

- Volume of affected extremity(ml)
  - *This target is measured non-invasively by perometry and MRI*

### 6.2 Secondary targets:

- Volume of affected extremity immediately after application of compression (ml)
  - *This target is measured non-invasively by perometry and MRI*
- Quality of life by SF-12 (short form 12) questionnaire
- Handling and wearing comfort of compression stockings in everyday life by questionnaire "*Tragekomfortbogen*" (comfort of wearing questionnaire)

## 7 Study design

### 7.1 Monocentric / multicentric

This is a monocentric interventional comparative therapy study with prospective data acquisition.

## 7.2 Study arms: intervention/control

This is a single group study with crossover components. Participants receive randomly and double-blinded either class I compression stockings or class II compression stockings. After four weeks, an exchange of compression classes takes place, so that all participants wear both classes of compression stockings within eight weeks.

## 7.3 Randomization

Randomization of patients is done with regard to the order of compression classes of the compression stockings. Patients are randomly assigned to compression class II or I for the first four weeks of compression therapy.

## 7.4 Blinding

This is a double-blind study. Neither investigator nor patient know the compression class (class I versus class II) of the compression stockings used in the different investigation periods in this patient.

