### ***Investigation day 28***

Participants fill out the SF-12 questionnaire. Then a measurement of the volume of the affected extremity is performed by perometry and MRI. First without any compression stocking and afterwards with both individualized compression stockings of class I and II.

This is followed by a four-week treatment with one of the two compression stockings, whereby the selection of compression class will be double-blinded.

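### Blinding is described only for class I versus class II; nothing masks whoever derives the day-28 MRI volumes for the stocking-versus-none comparison

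*Combined protocol and SAP*

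**What the plan says.** Section 5.2 labels the trial a "prospective, monocentric, double-blinded, non-invasive, interventional single group study". Section 7.4 says what the label means: "Neither investigator nor patient know the compression class (class I versus class II) of the compression stockings used in the different investigation periods". Section 7.3 adds "Randomization of patients is done with regard to the order of compression classes of the compression stockings". Section 7.2 and the day-28 and day-56 paragraphs of section 9.2 connect the blinding to the two four-week wear periods. In the day-28 paragraph the term describes only how the stocking for the following four weeks is chosen.

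The primary target in section 6.1 is the volume of the affected extremity, by perometry and MRI. Sections 5.1 and 9.3 speak instead of the volume of the malformation. For day 28, section 9.2 says "Then a measurement of the volume of the affected extremity is performed by perometry and MRI", in this order: "First without any compression stocking and afterwards with both individualized compression stockings of class I and II". The paragraphs for days 56 and 84 list questionnaires only.

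Section 11 tests each treatment against baseline with Wilcoxon signed rank tests, compares the two classes by linear regression with baseline adjustment, and sets the significance level at 0.05. Section 8.2 plans about 25 patients. Section 4 states that a relevant effect on malformation volume is expected.

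No section says who operates the perometer, who derives volumes from the MRI, or whether either is masked to the condition being measured.

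**The concern.** The primary hypothesis in section 5.1 is that class I compression already has a relevant effect on volume. In the text as scheduled, the data that bear on it are the day-28 volumes with and without a stocking. The blinding statement concerns a different contrast, class I versus class II.

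This matters because the direction of the hoped-for result is evident in advance and no untreated parallel group exists in which a systematic reading error would cancel. If the volume is that of the malformation, someone or some procedure must decide where the lesion ends on the image. A reader who knows which scan was taken under compression could shift that boundary slightly and consistently, and the paired test would treat the shift as a treatment effect.

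**Working it through.** **Step 1. Which comparisons does the stated blinding reach?**

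| Comparison | Where the data arise | Reached by section 7.4? |
|---|---|---|
| Class I versus no stocking, volume | Day 28 | No; the statement concerns class only |
| Class II versus no stocking, volume | Day 28 | No; same reason |
| Class I versus class II, volume | Day 28 | Unclear; depends on whether day 28 counts as an investigation period and on whether the stockings are coded then |
| Class I versus class II, questionnaires | Days 56 and 84 | Yes, as stated |

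The Wilcoxon tests in section 11 that concern volume are the first two rows.

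**Step 2. Could the condition be recognised?** The no-stocking measurement is fixed as first, so the acquisition time or scan order identifies the baseline scan to anyone who is shown it. No order is given for the two stockings, because section 7.3 randomises the wear periods and does not mention the day-28 measurements. At the measurement itself, stocking or none is plain to the patient and to whoever takes it, whether by perometry or MRI. Only the later derivation of a volume from stored MRI images can be masked.

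**Step 3. How sensitive is the test to a systematic shift?** The plan gives no effect size, SD, power or reading error, so it has no figure to reproduce, and what follows is an illustration.

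Inputs: n = 25 (section 8.2); level 0.05 (section 11), taken as two-sided because the plan does not say. Assumptions: normally distributed paired differences with SD 1, no true effect, and a constant reading shift of b SDs. n = 20 is added as an assumed loss of patients, since no dropout rate is given.

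Calculation: 20,000 simulated trials per row, with the Wilcoxon signed rank test applied to each. The simulation standard error is at most √(0.25/20,000) = 0.0035. The cross-check is the normal approximation Φ(b√n − 1.96) + Φ(−b√n − 1.96). For b = 0.2 and n = 25, b√n = 0.2 × 5 = 1.0, which gives Φ(−0.96) + Φ(−2.96) = 0.170.

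| Assumed shift b (SD) | Simulated, n = 25 | Normal approximation, n = 25 | Simulated, n = 20 |
|---|---|---|---|
| 0 | 0.048 | 0.050 | 0.046 |
| 0.1 | 0.074 | 0.079 | 0.072 |
| 0.2 | 0.156 | 0.170 | 0.129 |
| 0.3 | 0.283 | 0.323 | 0.239 |
| 0.5 | 0.647 | 0.705 | 0.546 |

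The approximation runs somewhat higher, as expected for a z-test with known SD compared with a rank test. Both show the same pattern: 0.1 SD does little, while 0.3 SD or more would seriously damage the test. The table says nothing about whether a shift exists.

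**The case against.** A reader might infer more than the documents support, in four ways.

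- **That the volumes are read with the condition known.** The plan does not say this. Scan order reveals the condition only to someone who is shown it, and an independent, masked reader is neither described nor excluded. The plan also never mentions outlining or segmentation, so how much judgement is involved is unknown. This stands, and it limits the point to a missing safeguard.
- **That the double-blind claim is false.** Section 7.4 confines the claim to class I versus class II, and the plan nowhere claims that stocking versus none is masked. This stands. The label in section 5.2 is unqualified, but its definition follows in section 7.4.
- **That the questionnaires are unblinded because patients try both stockings on day 28.** The day-28 SF-12 is completed before those measurements. For days 56 and 84 the trial fitting has taken place, but nothing shows that patients can tell the classes apart, and a crossover exposes everyone to both in any case.
- **That day 28 is beyond doubt the primary time point.** Sections 5.1 and 6.2 list volume immediately after application as secondary, which is a fair description of a day-28 stocking measurement, and section 6.1 gives no time for the primary volume. Section 9.4 allots day 28 about half an hour and day 0 about three hours, although section 10.1 puts the MRI examination at 20 minutes. Figure 1 is not available here and may add detail. Still, section 9.2 schedules volume on no other day, so whether the volume is called primary or secondary, the same day-28 contrast lacks masking.

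It is also fair to say that relabelling scans does nothing for perometry, and that the assumed shifts have no source in the plan.

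**Conclusion.** The point holds in limited form. The plan describes blinding to compression class and provides none for whoever derives the MRI volumes in the stocking-versus-none contrast, which is the contrast that its Wilcoxon tests of volume address. The effect on the result cannot be sized from the documents. Under the assumptions above, the false-positive rate at n = 25 runs from 7.4% for a shift of 0.1 SD to 64.7% for 0.5 SD, and whether any shift would occur is unknown. This is an inexpensive improvement worth making. It does not show that the volumes will be biased.

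Masking would not cure everything: because baseline is always measured first, condition and measurement order remain confounded however the images are read.

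**What to change.** In sections 7.4 and 9.2, state who derives the MRI volumes, and require three things: condition, order and time labels are removed from each patient's three day-28 scans; the scans are shuffled before the person already assigned to the task derives the volumes; and the codes are opened only after all volumes are saved.

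In sections 5.2 and 7.4, state that double-blind refers to class I versus class II only, and that stocking versus no stocking is not masked when the measurement is taken, by perometry or MRI.

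Cost: relabelling about 25 × 3 = 75 scans and a few sentences of text; no additional reader, visit or patient. Downside: masking may be only partial if the stocking shows on the image, and the plan should acknowledge this. Asking patients and investigators to guess the class at days 56 and 84 is optional and is not needed for this point.
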